### Statistical Approaches

Descriptive statistics will be generated to report the percentage of variants relative to the total enrolled cohort and to the control populations (European and Italian), stratified by disease (PD, parkinsonism, AD, FTD, YOD, ALS, and MCI), individual genes, and specific mutations.

Molecular–genetic data (single variants or variant groups) and clinicopathological data (diagnosis, disease stage, prognostic/predictive parameters, survival) will be analyzed using both numerical and graphical approaches. Frequency and contingency tables will be constructed, and statistical indices (means, percentiles, standard deviation) will be computed. Data will be visualized through histograms, boxplots, and scatterplots. Appropriate statistical tests—including t-tests, Fisher's exact test, and others depending on the formulated hypotheses—will be applied. Enrolled patients will be monitored through active follow-up as part of routine diagnostic care. Data regarding disability progression, disease course, and overall survival will be analyzed by diagnosis, mutation, or mutation combinations, as well as treatment received, using Kaplan–Meier survival analysis.

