### 3.1 Sample Management

- **Molecular analyses** will be performed using state-of-the-art technologies, in particular next-generation sequencing (NGS) of both second- and third-generation (short-read [SR] and long-read [LR]) platforms for DNA and/or RNA sequencing at the Genoa and Aosta (CMP3VdA) sites of the Istituto Italiano di Tecnologia Foundation.
- **NGS analyses of single genes, gene panels, clinical exome, and/or whole exome (WES)**—when indicated in the clinical management of these patients—will be carried out at the laboratories of IRCCS Policlinico San Martino (Genoa) and Fondazione IRCCS Policlinico Cà Granda (Milan). When necessary, these may also be performed at the IIT sites in Genoa and Aosta (CMP3VdA).
- **Proteomics, metabolomics, and lipidomics analyses:** Laboratory selection is ongoing to identify centers able to perform these investigations in accordance with the quality standards imposed by the project. Once identified, relevant ethical committees will be notified.
- **Data management and privacy:** The study's principal investigator is responsible for ensuring participant privacy. Study data will be recorded in a validated Data Management System via an electronic Case Report Form (eCRF), provided by the Scientific Directorate of IRCCS Policlinico San Martino (Genoa) and Fondazione IRCCS Policlinico Cà Granda (Milan). The REDCap (Research Electronic Data Capture) platform will be employed. The REDCap consortium comprises >1,000 institutional partners worldwide and supports secure web-based applications for research data collection. REDCap enables rapid and secure creation/management of online databases and is currently used for >110,000 projects with ~150,000 users across multiple research fields.  
For this study, REDCap will enable:
  - a) user-level identification with role-based access restrictions;
  - b) real-time data integrity validation;
  - c) patient de-identification prior to data export;
  - d) centralized data storage with daily backup on secure servers within the IT infrastructure of IRCCS Policlinico San Martino and Fondazione IRCCS Policlinico Cà Granda.
- **Biobanking:** Within the NeurOmics project, the Biological Resource Center (CRB) of IRCCS Policlinico San Martino and the Telethon Biobank of Fondazione IRCCS Policlinico Cà Granda will coordinate the collection, processing, and short- and long-term storage of samples, as well as their redistribution.

Specifically, the CRB will:

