##### Secondary Objectives

1. Identify causative or susceptibility genomic variants and provide accurate genetic counseling to patients and families.
2. Investigate associations between pathogenic variants in neurodegeneration-related genes and systemic comorbidities to inform prevention and early treatment.
3. Identify and characterize molecular markers (genes, transcripts, proteins, pathways) commonly dysregulated across different neurodegenerative diseases (e.g., cross-disorder gene overlap).
4. Identify cross-talk between known causative/susceptibility variants and additional transcripts/proteins/pathways influencing penetrance/expressivity of neurodegenerative disorders.

This study lays the foundation for defining homogeneous patient subgroups with combined clinical and genomic features, ultimately enabling personalized therapeutic strategies.

Given the sample size, disease-specific targeted studies may be conducted on selected subgroups. For example in Parkinson's disease, transcriptomic analyses will be performed in early-onset PD cases to detect expression or splicing defects in known PD genes, thereby revealing candidate genes with cryptic pathogenic variants through genome–transcriptome integration. Genetic data from PD patients will also be used to investigate associations between excess rare variants in predefined gene clusters (e.g., protein misfolding, mitochondrial dysfunction/oxidative stress, endolysosomal defects) and clinical phenotype, stratifying patients by progression rate: rapid progression (Hoehn & Yahr  $\geq 2.5$  at 5 years) versus slow progression (Hoehn & Yahr  $\leq 1$  at 5 years).

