### DNA Analysis with Nanopore Technology

Depending on research outcomes and project requirements, a subset of cases within this study may be sequenced using third-generation Oxford Nanopore Technologies (ONT). This approach may be particularly useful for improved characterization of structural variants, methylation profiling, validation purposes, and other specific analyses.

ONT provides a suite of analysis tools. For DNA sequencing, ONT currently recommends the Guppy basecaller, which is the most performant for initial basecalling. For alignment of sequencing reads to the reference genome, Lra will be employed, while SNV calling will be performed using Clair3.

For structural variant detection, alignment will be performed with Lra, and variant calling with CuteSV.

ONT technology also enables haplotype phasing, allowing determination of the allele on which a variant is located. This will be performed using the WhatsHap tool.

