### RNA Analysis

RNA sequencing (RNA-Seq) data, generated using commercially available platforms and those installed at CMP3VdA laboratories (currently Illumina and/or ONT), may be used to investigate gene expression and potential correlations between non-coding variants and expression changes. Expression quantitative trait loci (eQTLs) highlight variants that, although not altering protein structure, may affect transcriptional regulation and gene function. Additional analyses of transcript modifications, such as RNA methylation, may also be performed.

Gene expression analyses will be carried out using the DESeq2 package in R^81.

RNA sequencing with ONT technology further enables characterization of transcript isoforms generated by alternative splicing, in addition to quantifying expression. For instance, in Alzheimer's disease, certain TAU isoforms resulting from alternative splicing have been associated with increased disease risk.

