## 7.4 Statistical Analysis

### Sample Size

Given the nature of this study, sample size is not determined by a formal statistical power calculation but rather by projections of i) the number of patients with neurodegenerative diseases expected to be referred to the two experimental centers during the 10-year project period, and ii) an estimated compliance rate of approximately 80%.

We anticipate enrolling at least 1,000 patients with neurodegenerative diseases, distributed approximately as follows:

- a) Parkinson's disease (PD): ~30% of cases
- b) Parkinsonism: ~5% of cases
- c) Dementias:
  - Alzheimer's disease (AD): ~30% of cases
  - Frontotemporal dementia (FTD): ~10% of cases
  - Young Onset Dementia (YOD): ~5% of cases
  - Mild Cognitive Impairment (MCI): ~5% of cases
- d) Amyotrophic lateral sclerosis (ALS): ~15% of cases.

Additionally, ~200 geriatric controls with negative neurological evaluation and negative family history of neurodegeneration will be enrolled as internal controls.

The projected cohort of ~1,000 patients is based on the epidemiology of neurodegenerative diseases observed at IRCCS Policlinico San Martino (Genoa) and Fondazione IRCCS Policlinico Ca' Granda (Milan). The expected distribution across disease categories should allow reliable characterization of clinical and molecular subgroups.

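### Variant percentages are taken over everyone enrolled, which understates variants resolved only by assays that some patients receive

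*Protocol*

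**What the plan says.** **Denominator.** Section 7.4, Statistical Approaches, plans descriptive statistics "to report the percentage of variants relative to the total enrolled cohort and to the control populations (European and Italian), stratified by disease", then by gene and by mutation. It makes no exception for patients who lacked a given assay.

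**Study-wide assay.** Sections 3 and 5 plan whole-genome sequencing (WGS) for the study as a whole. The Illumina pipeline in section 7.3 calls SNVs, indels, structural variants, rearrangements and CNVs, and a separate subsection describes consensus calling of structural variants from short reads.

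**Assays given to some patients.**
- Long reads: section 7.3 says that "a subset of cases within this study may be sequenced using third-generation Oxford Nanopore Technologies (ONT").
- RNA: section 7.3, RNA Analysis, says that RNA-Seq data "may be used to investigate gene expression and potential correlations between non-coding variants and expression changes". The concrete plan, in section 5, is that "transcriptomic analyses will be performed in early-onset PD cases to detect expression or splicing defects in known PD genes".
- Single-gene, panel and exome tests: section 3.1 provides these "when indicated in the clinical management of these patients". Section 7.2 puts the centres' diagnostic genetic results into the CRF and REDCap.

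**Size.** "We anticipate enrolling at least 1,000 patients with neurodegenerative diseases", with no number or fraction for any of these subsets. The same subsection says that "sample size is not determined by a formal statistical power calculation".

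**The concern.** A percentage of carriers needs a denominator of people in whom the variant could have been seen. If a variant shows up only on long reads or in RNA, a patient without that assay is unknown, not negative. Dividing by everyone enrolled treats the unknowns as negatives, so the percentage can only go down.

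Two uses of the table are at stake. The percentages are to stand beside European and Italian control percentages. They are also split by disease, and one secondary objective looks for markers shared across diseases. If assay coverage differs between diseases, two diseases with the same true frequency will show different percentages.

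The affected classes are not purely hypothetical. Primary objective 1 names repeats, but the list of classes called from Illumina data does not. Section 7.2, Sequencing, credits long reads with better resolution of short repeat units, repeat-rich DNA and large inversions. The gene listed first for ALS in section 1.1, also named there for FTD, is described in a title in the protocol's own bibliography as a hexanucleotide repeat expansion. The protocol does not say which platform will call it.

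**Working it through.** The plan states no variant percentage and no assayed fraction, so there is no figure of its own to reproduce.

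**Inputs.** N = 1,000 enrolled patients (section 7.4, Sample Size). PD is about 30% of these, so 0.30 × 1,000 = 300. The fraction assayed, f, and the true carrier frequency, p, are not in the document. I assume p = 2% and vary f.

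**Formula.** For a variant seen only by the subset assay, and a subset whose frequency is p:

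- carriers found = p × f × N
- percentage over enrolled = (p × f × N) / N = p × f
- percentage over assayed = (p × f × N) / (f × N) = p

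**Results with p = 2%, N = 1,000**

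| f (assumed) | Assayed | Carriers found | Over enrolled | Over assayed |
|---|---|---|---|---|
| 1.0 | 1,000 | 20 | 2.00% | 2.00% |
| 0.8 | 800 | 16 | 1.60% | 2.00% |
| 0.5 | 500 | 10 | 1.00% | 2.00% |
| 0.2 | 200 | 4 | 0.40% | 2.00% |
| 0.1 | 100 | 2 | 0.20% | 2.00% |

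**Within one disease.** The same rule applies inside a stratum. If 60 of the roughly 300 PD patients had RNA-Seq (an assumed count), f = 60/300 = 0.2 and the PD percentage would be one fifth of the true one.

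**Across diseases.** With p = 2% in both, and assumed coverage of 0.5 in one disease and 0.2 in another, the table would show 1.0% and 0.4%.

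**Against controls.** Suppose that cases and controls both have p = 2%, and that all controls had the same assay. The apparent odds ratio at f = 0.5 is (0.010/0.990) / (0.020/0.980) = 0.49. At f = 0.2 it is (0.004/0.996) / (0.020/0.980) = 0.20. This is an illustration only. Table 1 lists WGS and WES resources and no long-read or RNA-Seq controls. For gnomAD it lists structural variants on 10,738 subjects against 76,156 genomes, which is 10,738/76,156 = 14.1%.

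**Where the bias vanishes.** For variants callable from study-wide short-read WGS, f is close to 1 and p × f is close to p.

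**The case against.** The strongest reply is that most of the variant table is unaffected. WGS is the study-wide assay, and short reads yield structural variants as well as SNVs, indels and CNVs. Long reads are offered partly for better characterisation and validation. Splicing variants are sought in genomic as well as transcriptomic data, and RNA in early-onset PD serves partly to point to a variant that lies in the genome data. Panels and exomes cover regions that WGS also reads. All of this stands. A reader might infer that structural and splicing variants as whole classes are visible only in assayed subsets, but the protocol does not support that. The point concerns only what the subset assays add.

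The reply can also say that the table is descriptive. Sections 7.3 and 7.4 handle control comparisons separately, through allele frequencies, variant counts per sample, odds ratios and q-values. That stands too, and it limits the consequence.

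It may be said that evaluable denominators belong in a statistical analysis plan. Often they do, but here the protocol names a denominator, so a plan that used assayed patients would have to depart from it.

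Three further inferences are tempting and should not be made:
- **Internal controls in the denominator.** The protocol says that geriatric controls with "negative family history of neurodegeneration will be enrolled as internal controls". However, the same subsection calls the cohort about 1,000 patients and adds the controls on top.
- **Each disease's carriers divided by the whole cohort.** The percentages are stratified by disease, which ordinarily means within disease.
- **Controls fully assayed for these variants.** Table 1 does not show this. The difference in assay between cases and controls is a separate problem, which a new denominator alone does not solve.

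**Conclusion.** The point holds in a limited form. As written, section 7.4 understates the percentage of any variant resolved only by an assay that some patients receive, and the multiplier is the fraction assayed. The direction follows from the text. The size does not: the percentage is halved at f = 0.5, falls to one fifth at f = 0.2, and is almost unchanged for variants callable from short-read WGS. A reader might infer a several-fold understatement. Threefold or more would need f of one third or less, and no figure in the protocol establishes that.

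The working assumes that the assayed patients have the same true frequency as the rest of their disease group. If the subset is selected, as with early-onset PD, the percentage among assayed patients describes that subset only.

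This is worth correcting because the change is nearly free. It does not threaten the study's main association analyses.

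**What to change.** In section 7.4, Statistical Approaches, replace the total enrolled cohort as the reference with: *relative to the patients with that diagnosis who were successfully assayed by a method able to detect that variant, reported by platform with numerator and denominator.* Add: *Percentages are compared with a control population only for variants detectable by the same type of assay in that population.* Where the subset was selected, say how, and do not extend its percentage to the whole disease group.

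In practice this needs a record for each patient of which assays were completed successfully, for example a flag in REDCap. No new patients or samples are required.

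The cost is smaller denominators and wider intervals for the subset assays. With p = 2%, the standard error is √(0.02 × 0.98 / 1,000) = 0.44 percentage points if all 1,000 are assayed, and √(0.02 × 0.98 / 200) = 0.99 points if 200 are. That width reflects the information actually collected.

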The complexity of ALS is underscored by the failure of more than 40 randomized controlled trials aimed at identifying effective disease-modifying therapies. Currently, riluzole remains the only approved disease-modifying drug in most European countries; its antiglutamatergic properties prolong survival by approximately six months. More recently, the FDA approved tofersen for patients carrying *SOD1* mutations.

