#### Clinical data collection

Following consent, clinical data will be collected at participating Units and managed through REDCap. Case report forms (CRFs) will specify disease-specific data. At Visit 1, the following will be recorded:

- Sex
- Age
- Medical history
- Neurological examination
- Neuropsychological profile
- Neuroimaging findings
- Previous treatments
- Planned treatments

#### - Visit 2

If consent is given, patients/legal representatives will be informed of clinically relevant genetic variants identified. Variants associated with risk of developing other conditions (subject to confirmatory testing) will be disclosed during genetic counseling with psychological support. Patients will also decide whether information should be extended to relatives.

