#### - Follow-up visits

Subsequent follow-up visits will coincide with routine clinical visits in Neurology and Geriatrics Units at Genoa and Milan centers.

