## 7.2 Sample Collection and Processing

### - Genomic data collection

Molecular and genetic diagnostic data generated at Genoa and Milan centers will be entered into the CRF and REDCap. Genomic data generated by IIT-CMP3VdA will be stored at the Engineering D.Hub data center in Pont Saint Martin (Aosta), with backup in Vicenza.

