##### - DNA analysis using Illumina technology

For genomics, DNA variants identified will be analyzed jointly by CMP3VdA and the clinical units in Genoa and Milan. The analytical pipeline will generate the following files:

1. **FASTQ** – containing raw sequencing reads and per-base quality scores; the starting point of bioinformatic analyses.
2. **BAM** – containing mapped reads aligned to the human reference genome.
3. **VCF/BCF** – containing identified variants for each individual.

Pipeline steps:

- a) Quality assessment, filtering, and trimming of raw reads.
- b) Read alignment to the reference genome.
- c) Identification of SNVs, indels, structural variations (SVs), rearrangements, and copy number variations (CNVs).
- d) Generation of a comprehensive variant database.
- e) Compilation of control population variants and allele frequency tables.
- f) Comparison of patient-specific variants and allele frequencies with control populations and public cohorts.
- g) Prediction of variant effects and association with genomic features.
- h) Prioritization of patient-specific variants and their association with neurodegenerative disorders, leading to genomic-based stratification.

The pipeline employs standard tools, notably **GATK (Genome Analysis ToolKit)** from the Broad Institute, widely considered the gold standard for variant analysis. As certain GATK tools are computationally intensive, IIT uses NVIDIA GPUs and **Clara™ Parabricks** software for accelerated processing, achieving a 15–20× reduction in runtime for mapping and variant calling.

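### For known, clinically relevant variants, later disability scores are taken in centres whose clinical units can know the genotype, and the planned analysis by mutation cannot detect any effect of that knowledge

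*Protocol*

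**What the plan says.** Five places in the protocol bear on this.

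- **Outcome and grouping (7.4, Statistical Approaches).** "Data regarding disability progression, disease course, and overall survival will be analyzed by diagnosis, mutation, or mutation combinations". The same sentence adds treatment received as a grouping factor and names Kaplan–Meier analysis. The data source is routine care: "Enrolled patients will be monitored through active follow-up as part of routine diagnostic care".
- **Who analyses the variants (7.3, DNA analysis using Illumina technology).** "DNA variants identified will be analyzed jointly by CMP3VdA and the clinical units in Genoa and Milan".
- **Where genetic results are held (7.2, Genomic data collection).** "Molecular and genetic diagnostic data generated at Genoa and Milan centers will be entered into the CRF and REDCap". REDCap also manages the clinical data (7.1, Clinical data collection).
- **Who is told (7.1, Visit 2).** "If consent is given, patients/legal representatives will be informed of clinically relevant genetic variants identified".
- **Who sees the patient afterwards (7.1, Follow-up visits).** "Subsequent follow-up visits will coincide with routine clinical visits in Neurology and Geriatrics Units at Genoa and Milan centers".

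The primary objectives in Section 5 include correlating genetic alterations with clinical phenotype (objective 2) and studying the impact of molecular mechanisms on progression (objective 5). Section 5 also describes a Parkinson's disease (PD) analysis relating an excess of rare variants to progression rate, defined by Hoehn & Yahr stage at 5 years.

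**The concern.** A comparison of progression between carriers and non-carriers is sound only if the score does not depend on knowing who is a carrier. Hoehn & Yahr, UPDRS-III and daily-living scales depend on the judgement of a rater or on what the patient or informant reports. Once a clinically relevant variant is known, a rater may look harder for the course expected of it, or a patient may report function differently. This could exaggerate a genotype-progression association, create one, or weaken a real one.

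The protocol describes neither raters unaware of genotype nor a record of when the result became known. Without that date, assessments made before and after the result cannot be separated later, whatever a statistical analysis plan says. A difference in progression by mutation could then be genetic, a rating effect, or both, with no means of telling which.

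**Working it through.** **Step 1. Does the protocol allow knowledge of genotype to reach the scores?**

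| Link | Place | Finding |
|---|---|---|
| Clinical units learn the variants | 7.3 | Joint analysis with the sequencing centre |
| Patient learns the variant | 7.1, Visit 2 | With consent, clinically relevant variants only |
| Later scores come from the same centres | 7.1, Follow-up visits | Routine visits after Visit 2 |
| Scores are compared by mutation | 7.4 | No separation by date of knowledge |
| Pseudonymisation | Section 10 | A privacy measure; clinical staff directly involved may hold the link |
| Role-based REDCap access | 3.1 | Not said to hide genotype from raters |

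The chain is complete at the level of units, and neither privacy measure breaks it. Section 3.1 also allows clinically indicated panel or exome tests at the hospital laboratories, so for some patients the result may be known before Visit 2.

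**Step 2. Which results are exposed?**

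- *Exposed:* rater- or patient-dependent scores made after the result is known, for known and clinically relevant variants.
- *Largely unexposed:* Visit 1 severity, because the neurological examination and neuropsychological profile are recorded at the visit where blood is drawn, before study sequencing; novel and non-coding variants, for which a rater has little expectation; and overall survival, which is not a rating.
- *Unclear:* the 5-year Hoehn & Yahr stage. The protocol does not say from which time point the 5 years run, so this score may fall before or after the result.

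**Step 3. How large could it be?** The protocol gives no figure to reproduce: the sample size is a recruitment projection without alpha, power, effect size or SD. What follows is an illustration only.

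Inputs from the protocol:
- PD is about 30% of 1,000 (7.4), so 300 patients.
- A genetic cause is found in about 10% of PD (Section 1), so 300 × 0.10 = 30 carriers and 270 non-carriers.

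Assumptions: no true genotype effect, a two-sided 5% test of mean scores, and knowledge of genotype shifting every carrier's score by d SD.

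Shift in the test statistic = d × √(n₁n₀/(n₁+n₀)) = d × √(30 × 270/300) = d × √27 = 5.196 d.

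Rejection probability = P(|Z + shift| > 1.96).

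| d (assumed) | Shift | False-positive rate |
|---|---|---|
| 0 | 0 | 5.0% |
| 0.1 | 0.520 | 8.1% |
| 0.2 | 1.039 | 18.0% |
| 0.3 | 1.559 | 34.4% |

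Milder assumptions give less, for the same d of 0.1, 0.2 and 0.3:
- 15 carriers and 285 non-carriers: 6.6%, 11.7%, 20.5%.
- 30 carriers, but only half the shift reaching the analysed outcome: 5.8%, 8.1%, 12.2%.
- One mutation with 5 carriers (assumed) and 295 others: √(5 × 295/300) = 2.217, giving 5.6%, 7.3%, 10.2%.

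The q-value correction in 7.4 deals with multiplicity. It does not remove a systematic shift in the scores.

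**The case against.** The case on the other side has several parts.

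- **Unmasked follow-up is inherent in an observational study run in routine care, and sensitivity analyses are commonly left to a statistical analysis plan.** Both are true. But the date on which a result became known is a data-collection item. If it is not captured during the 10-year study it may not be reliably recoverable, and no later plan can use it.
- **A reader might infer that the same person classifies variants and rates patients.** The protocol does not say so. The overlap is between units, and nobody is named as the discloser at Visit 2.
- **A reader might infer that all genotype-phenotype results are compromised, including the severity correlations of objective 2.** They are not. Visit 1 severity precedes study sequencing, and disclosure needs consent and covers only clinically relevant variants. The PD entry criterion of at least 24 months of longitudinal assessments may itself refer to data that precede the study.
- **A reader might infer that survival by mutation is distorted by genotype-directed treatment, because Section 1.1 says "the FDA approved tofersen for patients carrying" one gene's mutations.** The support is thin. That is an FDA approval, Section 1.1 describes a single other drug as approved in most European countries, no passage says participants will receive such treatment, and 7.4 already plans analysis by treatment received.
- **A reader might infer that associations will be inflated.** The direction is unknown.
- **The illustration is near a worst case.** This stands. It pools all PD mutations, supposes every carrier is known and fully shifted, and uses a test of means where 7.4 names Kaplan–Meier analysis.

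What remains is narrow: later scores, for known and clinically relevant variants.

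**Conclusion.** The point holds in this limited form. After a clinically relevant variant is known, rater- or patient-dependent scores from the same centres can be affected by that knowledge, in either direction, and the analysis in 7.4 has no means of detecting it. The conclusion rests on the unit-level overlap and on the absence of any stated masking or date field; it does not require that any one person both analyses variants and rates.

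The size cannot be derived from the protocol. The PD rates of 8%, 18% and 34% depend on assumed shifts and mark the upper end; the milder settings above run from 5.6% to 20.5%. This is a worthwhile and inexpensive improvement, not a defect that invalidates the study. It bears mainly on objective 5 and on progression by known mutation.

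**What to change.** 1. **Add one eCRF field:** the date the treating unit first had each patient's genetic result, whether positive or negative, and whether from a clinical test or from the study. Recording negative results too means the date is defined for carriers and non-carriers alike.
2. **Add one sensitivity analysis to 7.4.** Keep all follow-up in the main analysis. For each genotype-progression result, pre-specify a repeat restricted to assessments before that date in both groups. Report the estimate with its confidence interval as a check of consistency, not as a condition for making a claim.

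No masking of treating clinicians, change to disclosure or change to care is needed. A before/after-disclosure model term is not proposed, since it would be confounded with disease duration within carriers.

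The cost is one date field and one extra analysis. The restricted analysis will have fewer assessments and wider intervals, and for late outcomes such as the 5-year Hoehn & Yahr stage it may be uninformative if most results arrive earlier.

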#### 4. STUDY DURATION

The study will have an overall duration of **10 years**. Follow-up assessments will be conducted periodically, as per routine clinical practice for each condition under investigation.

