**PARKINSON'S DISEASE (PD)**

**Inclusion criteria**

- Signed written informed consent from the patient and/or legal representative (Appendix X);
- Age  $\geq 18$  years;
- Clinical diagnosis of PD according to revised MDS criteria, as follows:

- Predominant motor presentation with bradykinesia plus resting tremor and/or rigidity;
- MMSE  $>24$ , with preserved (MCI) or mildly impaired (mild dementia) instrumental daily living activities (CDR 0.5–1);
- Absence of significant neurological/systemic comorbidities or structural abnormalities indicative of other causes of cognitive impairment;
- Imaging findings:
  - a) Normal structural brain imaging;
  - b) Striatal DAT binding reduction on SPECT DAT-SCAN;
- Availability of longitudinal clinical assessments, including motor scales (e.g., UPDRS-III, Hoehn & Yahr), MMSE/MOCA, and daily living activities, for at least 24 months.

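### Section 7.4 applies Kaplan–Meier to disability progression that is seen only at routine visits, so unequal visit spacing between compared groups would shift the curves for reasons unrelated to disease

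*Protocol*

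**What the plan says.** Under Statistical Approaches in Section 7.4, the protocol says: "Data regarding disability progression, disease course, and overall survival will be analyzed by diagnosis, mutation, or mutation combinations", continuing "as well as treatment received, using Kaplan–Meier survival analysis". One method is therefore named for three outcomes and three grouping factors. The preceding sentence gives the data source: "Enrolled patients will be monitored through active follow-up as part of routine diagnostic care".

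Visit timing is set in two other places. Section 4 says: "Follow-up assessments will be conducted periodically, as per routine clinical practice for each condition under investigation". Section 7.1 says: "Subsequent follow-up visits will coincide with routine clinical visits in Neurology and Geriatrics Units at Genoa and Milan centers".

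The inclusion criteria for PD ask for "Availability of longitudinal clinical assessments, including motor scales (e.g., UPDRS-III, Hoehn & Yahr), MMSE/MOCA, and daily living activities, for at least 24 months". AD, FTLD and DLB carry a similar 24-month line, while ALS and MCI have none. None of these lines gives a spacing. The protocol contains no visit interval for any condition, no common assessment grid and no rule for dating progression between visits.

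**The concern.** A patient who crosses a threshold on a scale such as Hoehn & Yahr or MMSE does so at an unobserved moment between the last visit without progression and the first visit with it. Kaplan–Meier needs an exact event time, and with visit data the natural choice is the detecting visit, which is always on or after the true time. The delay grows with the gap between visits.

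A delay common to all groups does little harm to a comparison. Here timing follows the practice for each condition, and diagnosis is the first factor compared. A group seen less often would appear to progress later, even with full attendance and no deaths, so this is separate from loss to follow-up and from death as a competing event. Primary objective 5 concerns the impact of molecular mechanisms on disease progression, so the affected outcome is a central one.

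**Working it through.** **Inputs from the protocol.** The method, outcomes, grouping factors and visit timing are as quoted above. On duration: "The study will have an overall duration of 10 years", which is 120 months. For group sizes, with 1,000 patients, "Parkinson's disease (PD): ~30% of cases" gives 1,000 × 0.30 = 300, and ALS at about 15% gives 150.

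**Assumed, because the protocol does not state them.** Visit intervals of 3, 6 or 12 months; exponential progression times with medians of 12 to 60 months, identical in the compared groups; a two-sided 5% log-rank test. The plan has no figure of its own to reproduce.

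**Step 1: delay.** If visits come every d months and their phase is unrelated to progression, the delay is uniform between 0 and d, with mean d/2. This gives 3/2 = 1.5, 6/2 = 3 and 12/2 = 6 months. Simulation gave 1.5, 3.0 and 6.0.

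**Step 2: apparent median.** This is approximately the true median + d/2. Simulated values in months:

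| True median | 3-monthly | 6-monthly | 12-monthly |
|---|---|---|---|
| 12 | 13.5 | 15.1 | 18.3 |
| 24 | 25.5 | 27.0 | 30.1 |
| 36 | 37.6 | 39.1 | 42.2 |
| 60 | 61.7 | 63.2 | 66.2 |

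The spurious gap between two groups is about (d2 − d1)/2: 4.5 months for 3 versus 12, 3 months for 6 versus 12, and 1.5 months for 3 versus 6.

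**Step 3: false-positive rate.** 150 versus 300 patients, censoring at 60 months, 1,500 runs, no true difference:

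| Visit spacing (months) | Median 12 | Median 24 | Median 36 |
|---|---|---|---|
| 6 vs 6 | 0.05 | 0.05 | 0.06 |
| 3 vs 6 | 0.16 | 0.07 | 0.07 |
| 6 vs 12 | 0.40 | 0.15 | 0.12 |
| 3 vs 12 | 0.70 | 0.31 | 0.19 |

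In every unequal setting the group seen less often appeared to progress later.

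**Step 4: sensitivity to coding.** A second design used 150 per group, censoring uniform over 120 months, visit gaps of 0.6–1.4 times nominal and 400 runs. The result depends on whether follow-up without progression ends at the last visit or at the administrative date:

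- 3 vs 12 months, median 18: 33% or 48%, with apparent medians of 19.3 vs 24.2 months under last-visit censoring.
- 6 vs 12 months, median 18: 17% or 25%.
- 3 vs 12 months, median 30: 11% or 20%.
- Equal 3-monthly visits: about 4% (last-visit censoring).

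Further runs with 150 per group gave 34–51% for 3 vs 12 (median 18), 20–26% for 6 vs 12 (median 18), 6–7% for 3 vs 6 (median 30) and 4–7% for 6 vs 12 (median 60).

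**Step 5: does the remedy work?** An interval-censored Weibull model fitted to such data rejected in 3–6% of runs. The true times were exponential, a special case of the Weibull, so this is a favourable test. A Turnbull curve and a mixed model on repeated scores were not simulated.

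**The case against.** The strongest reply has four parts.

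*No interval and no test is stated.* This stands. Section 4 ties follow-up to each condition but does not say that spacing differs. A reader might infer that the protocol fixes different schedules by diagnosis, or that its log-rank tests lose their error control. It does neither: no log-rank test or significance level is named, and the tests are left to the hypotheses formulated. The shift in curves and medians needs no test, but its size cannot be placed from the documents.

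*Mutation and treatment comparisons are conjecture.* This largely stands. A reader might infer that disclosing results at Visit 2 changes how often carriers are seen. Section 7.1 describes disclosure and counselling and says nothing about visit frequency. What remains is pooling. Section 1.1 names C9orf72 under both FTD and ALS, so a mutation comparison across diagnoses would carry over any spacing difference between them.

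*Equal progression across diagnoses is a weak null.* This also stands. The measures differ by disease, no common progression event is defined, and the one explicit progression definition (Section 5, for PD) is a Hoehn & Yahr split at 5 years, not a time to event. The false-positive rates therefore illustrate the mechanism and do not predict the study's error rate. Estimated times by diagnosis would still be displaced by unequal amounts.

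*This belongs in the statistical analysis plan.* Only partly. Event definitions may well be there, and naming Kaplan–Meier does not exclude a supplementary analysis. But the protocol itself names the method and leaves visit timing to routine care, and the two fit poorly together.

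**Conclusion.** The point holds as a conditional one. Section 7.4 uses an exact-time method for an outcome observed only at routine visits without a common grid. The delay is about half the visit interval. It matters where spacing differs between compared groups, which the text makes a live possibility for diagnosis. For mutation or treatment it matters only through pooled diagnoses or an incidental difference in visit frequency. Overall survival, named in the same sentence, is unaffected if dates of death are known.

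The size rests entirely on assumed spacing, progression rates and a log-rank test. With similar spacing or slow progression, rejection under no true difference stays at about 5–7%. With 3- versus 12-monthly visits and a median of 18 months it is about 30–50%, and it is higher for faster progression. The documents do not say where in this range the study lies. The change is worth making because it is cheap and needs no extra visits.

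**What to change.** In Section 7.4:

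- Keep Kaplan–Meier for overall survival.
- Analyse scale-based progression as interval-censored, with the last visit without and the first visit with progression as limits, using a Turnbull curve and interval-censored regression. Alternatively, model the repeated scores on their actual assessment dates with a mixed model.
- Stratify mutation and treatment comparisons by diagnosis.
- Report visit spacing by compared group.
- Confirm that the eCRF captures the date of every follow-up assessment. Section 7.1 lists data items for Visit 1 only, so it should not be assumed that these dates are already in REDCap.

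The cost is a few sentences in 7.4, a check of the eCRF and a little more analysis work. Intervals may be somewhat wider. If visits are brought forward because a patient is worsening, standard interval-censored methods can keep some bias, and the reported visit spacing should be read with that in mind.
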